10.3 Vital Signs

Vital signs including systolic and diastolic blood pressure (mmHg), pulse rate (beats/min), temperature (°C), and respiration rate (breaths/min) will be listed for each subject.

For each vital sign parameter, absolute values and changes from baseline will be summarized descriptively by treatment and visit. For SMT+ Albutein 20% group, change from baseline to the pre-infusion timepoint will be summarized. Moreover, the difference between pre-infusion and post-infusion within each visit will also be summarized.

10.4 Physical Assessment

Physical assessment findings (normal and abnormal) will be listed for each subject and summarized by treatment and visit. Any clinically significant abnormality, as determined by the investigator, experienced by a subject during the clinical study and not already present at baseline will be reported as an AE.

11 Interim Analysis

No interim analysis is planned.

12 Changes in Planned Analysis

During the conduct of the study, protocol amendments and varying recruitment rates between countries introduced potential variables to the study that will be analyzed for relevance to interpreting the outcomes on the efficacy endpoints. Specifically, the following variables will be analyzed as described further in the subsections below:

- Addition of CLIF-C AD > 50 as an inclusion criterion

GRIFOLS	Bioscience Industrial Group	Number	IG1601	IG1601 Statistical Analysis Plan
		Version	2.0	
Number	IG1601 Statistical Analysis Plan	Status	Effective	
		Effective Date	09-Sep-2024	44 of 52

Number	IG1601	IG1601 Statistical Analysis Plan
Version	2.0	
Status		
Effective		

Effective Date	09-Sep-2024
Page	45 of 52

- Number of subjects recruited per country and region in Europe (East and West Europe) as a subgroup analysis. Time from start of screening to randomization with first dose of IP as a subgroup analysis.
- Changes in the analysis of longitudinal outcomes.

Rationale and plan for subgroup analysis based on CLIF-C AD score

CLIF-C AD, a specific prognostic score for hospitalized cirrhotic patients with acute decompensation (18), was not an entry criterion in the study until Protocol Amendment 4, Version 5. In this amendment, the enrollment criteria that subjects needed a CLIF-C AD score >50 at screening was added to increase event rates for the primary efficacy endpoint. A subgroup analysis on the primary and secondary efficacy endpoints will be conducted comparing “CLIF-C AD score >50 ” vs “CLIF-C AD ≤ 50 ”. This subgroup analysis is incorporated into the appropriate sections above (See [Section 9.1.4](#)). This subgroup analysis is intended to address whether the study intervention demonstrates any differential effect on endpoints based on CLIF-C AD scores at enrollment.

Rationale and plan for subgroup analysis based on country recruitment

Since this study is a large multinational study with varying rates of recruitment between countries, a subgroup analysis will be conducted for countries with reasonably large number of patients (30 patients). The objective of these analyses is to examine whether the patients in different countries benefit differently from the treatment possibly due to different standard medical treatment. This subgroup analysis is incorporated in the appropriate sections above (See [Section 9.1.4](#)). We do not conduct this subgroup analysis for countries with fewer patients because the model may not converge due to the fact that uncertainties in the parameter estimates become larger due to small sample size. For European countries an additional grouping based on the region in Europe the countries are located will be applied and subgroup analyses will be performed.

Rationale and plan for subgroup analysis based on time from start of screening to randomization with first treatment with IP

The time window from screening to first administration of Albutein 20% in the treatment arm has varied with protocol amendments. The final protocol amendment under which most of the patients were enrolled dictates that patients are randomized and receive first dose of IP within 3 days (72 hours) of start of screening, whereas earlier versions allow for the first dose of IP to occur more than 3 days (72 hours) after start of screening. To account for any possible differential treatment effect based on time to treatment with IP, a subgroup analysis will be done comparing subjects with time to randomization from start of screening ≤ 3 days vs time to randomization from start of screening >3 days. This subgroup analysis is incorporated in the appropriate sections above (See [Section 9.1.4](#)).

Discussion of the definition of TEAE in the SAP

In the protocol, a TEAE is defined as an AE which occurs between the start of study treatment and the final visit of the clinical study. In this SAP, TEAEs are defined as AE

with onset date/time on or after the subject's randomization date/time for SMT arm, and with onset date/time during or after the first dose administration for the SMT + Albutein 20% arm. For subjects in the SMT + Albutein 20% arm, the first dose is scheduled on the same day as randomization. The definition is modified because the treatment time after randomization entered in the EDC for subjects in the SMT arm may not be on day 1, which may cause bias in the comparison of TEAE between the two groups. The new definition assumes that subjects in the SMT group had been on the SMT treatment before entering the trial. The new definition intends to remove bias in the comparison of TEAE between two treatment groups.

Changes in the analysis of longitudinal outcomes

The MMRM will be used to analyze the longitudinal continuous outcomes [e.g., CLIF-C OF score, CLIF-C ACLF score, CLIF-C AD score, MELD score, EQ-5D-5L index score, EQ-5D-5L VAS score], and general linear model implemented in SAS Proc GENMOD will be used to analyze the longitudinal binary or ordinal outcomes [Child-Pugh Score, Incidence of disease-related complications, Incidence of insertion of TIPS for refractory ascites]. However, as stated in Section 9.1.2.3 of the protocol, exploratory endpoints would be analyzed by means of ANCOVA or Student's t tests (for normally-distributed variables), non-parametric Mann-Whitney U test (for non-parametric variables), and Fisher's exact test or Chi-square test (for binomial variables). The methods specified in the protocol are not suitable for longitudinal outcomes with missing data.

Adding Ethnicity as a new subgroup analysis

The Ethnicity is collected in EDC. To account for any possible differential treatment effect based on ethnicity, a subgroup analysis will be done comparing Hispanic subjects vs non-Hispanic subjects. This subgroup analysis is incorporated in the appropriate sections above (see [Section 9.1.4](#)).

GRIFOLS	Number	BIG-CL-SP-000319	
	Version	2.0	
	Status	Effective	
	Effective Date	09-Sep-2024	
	Page	46 of 52	

13 References

Appendix 1 – Schedule of Study Procedures and Events

		Treatment Period ^a				
		Screening	Day 1	Day 11, Months 1-11 ^b	Treatment Days ^c	Month 12 / Early Discontinuation
Inclusion/exclusion criteria	X	X				
Medical history & demographics	X					
Abdominal ultrasound	X ^k					
Endoscopic procedures	X ^l					
Urine pregnancy test	X					
Physical exam	X ^m		X ⁿ		X	
Randomization		X				
Vital signs ^e		X	X	X	X	
Ascites assessment	X	X	X		X	
Hepatic encephalopathy evaluation	X		X		X	
Hemodynamics assessment (MAP)	X		X		X	
Peripheral capillary oxygen saturation (SpO ₂)	X		X		X	
Weight		X	X	X	X	
Clinical laboratory assessments ^f	X	X	X		X	
Serum albumin concentration ^g		X	X		X ^r	
Record ACLF grade	X		X		X	
Systemic inflammation assessment ^h		X	X		X	
Illness severity scores evaluation ⁱ	X		X		X	
Quality of life assessment (EQ-5D-5L health questionnaire)		X	X ^o		X	
Prior and concomitant medications	X	X	X	X	X	X
Albumin infusion		X ^c	X ^c	X ^c	X ^r	
Assess TIPS insertion			X		X	
Albumin functional capacity assessment (albumin binding capacity)		X	X ^p		X	
Adverse events	X	X	X	X	X	X
Biomarker retains ^j		X	X ^o		X	
Liver transplantation, survival, cause of death data			X ^q		X	X

Abbreviations: ACLF = Acute-on-chronic liver failure; EQ-5D-5L = EuroQol 5 Dimensions 5 Levels; MAP = Mean arterial pressure; TIPS = Transjugular intrahepatic portosystemic shunt.

- a The treatment period will be up to 12 months.
- b Subjects will have assessments on Day 11 (± 2 days), Month 1 (± 2 days), and then monthly (± 2 days) for up to 12 months.
- c Subjects will be randomized (Day 1) within 3 days (72 hours) of Screening. Following randomizations, subjects in the SMT + Albutein 20% treatment group will receive the first infusion on the same day at the dose of 1.5 g/kg body weight (maximum 100 grams per subject). Thereafter, subjects will receive Albutein 20% infusions at the dose of 1.5 g/kg body weight (maximum 100 grams per subject) every 10 ± 2 days for the rest of the study.
- d Subjects who discontinue from the study early will have follow-up vital status assessments performed at Months 3, 6, and 12.
- e Vital signs include systolic blood pressure, diastolic blood pressure, heart rate, temperature, and respiratory rate. Vital signs will be measured immediately prior to and immediately after the end of the Albutein 20% administration in the SMT + Albutein 20% treatment group.
- f Clinical laboratory assessments will include hematology, chemistry, and coagulation performed by the central lab. At the Screening visit only, local laboratory tests will be performed in order to determine subject eligibility. Screening local laboratory test results will be kept in subjects' source documents but will not be entered into the eCRF.
- g Serum albumin concentration will be measured immediately prior to treatment. In the SMT + Albutein 20% treatment group, serum albumin concentration will also be measured immediately after the end of the Albutein 20% administration.
- h Systemic inflammation assessment includes testing for procalcitonin, WBC, and CRP.
- i Illness severity scores include CLIF-C OF score, CLIF-C AD score, CLIF-C ACLF score, MELD score, and Child Pugh score.
- j Biomarker retails will be drawn for potential analysis of cytokines (IL-6, IL-8, IL-10, and TNF α) found in the blood which are significantly correlated with disease activity. All clinical blood samples will need to be drawn first before biomarker retails are drawn.
- k Findings from abdominal ultrasounds performed in the last 6 months will be recorded.
- l Findings from endoscopic procedures performed in the last 6 months will be recorded.
- m Full physical examination (excluding breast and genitourinary examination).
- n Physical examination performed on Month 6 only.
- o EQ-5D-5L health questionnaire and optional collection for blood biomarker retails on Months 1, 3, 6, and 9. All clinical blood samples will need to be drawn first.
- p Assessed on Day 11 and Months 1, 3, 6, and 9.
- q Assessed on Months 3 and 6.
- r Month 12 Visit only.

GRIFOLS	Bioscience Industrial Group	Number	IG1601	Statistical Analysis Plan
		Version	2.0	Page
49 of 52	49 of 52	Effective Date	09-Sep-2024	
		Effective		

Appendix 2 – A rule for determining whether an AE with incomplete start date/time is TEAE

The following procedure will be used to determine whether an AE with incomplete start date/time is TEAE in the SMT + Albutein 20% treatment group. In the AE start/end date/time, the observed value in the lower time frame (day, hour, minute) will not be used if the value in a higher time frame (e.g., month) is missing.

Step 1: to determine whether an AE with incomplete start date/time is non-TEAE based on the AE end date/time in the SMT + Albutein 20% treatment group

- 1a. If the AE end year value is less than the treatment start year value, it is a non-TEAE
- 1b. otherwise, if years under comparison in step 1a) are equal, but the AE month value is less than the treatment start month value, the AE is a non-TEAE
- 1c. otherwise, if months under comparison in step 1b) are equal, but the AE end day value is less than the treatment start day value, the AE is a non-TEAE
- 1d. otherwise, if the days under comparison in step 1c) are equal, but AE end hour value is less than the treatment start hour value, the AE is a non-TEAE
- 1e. otherwise, if the hours under comparison in step 1d) are equal, but AE end minute value is less than the treatment minute value, the AE is a non-TEAE

Step 2: If the AE with incomplete start date cannot be determined to be non-TEAE based on the AE end date/time in step 1), the following conservative rule will be used to determine whether it is TEAE

- 2a. if the AE start year value is missing, it is an TEAE
- 2b. otherwise when the year of AE start date/time is not missing, it is a non-TEAE if the AE start year value is less than the treatment start year value, and the AE is a TEAE if the AE start year value is larger than the treatment start year
- 2c. otherwise, if the AE start year value is equal to the treatment start year value, but the AE start month value is missing, the AE is a TEAE
- 2d. otherwise, when the AE start month value is not missing, it is a non-TEAE if the AE start month value is less than the treatment start month value, and the AE is a TEAE if the AE start month value is larger than the treatment start month value
- 2e. otherwise, if the AE start month value is equal to the treatment start month value, but the AE start day value is missing, the AE is a TEAE
- 2f. otherwise, when the AE start day value is not missing, it is a non-TEAE if the AE start day value is less than the treatment start day value, and the AE is a TEAE if the AE start day value is larger than the treatment start day value
- 2g. otherwise, if the AE start day value is larger than the treatment start day value, but the AE start hour value is missing, the AE is a TEAE
- 2h. otherwise, when the AE start hour value is not missing, it is a non-TEAE if the AE start hour value is less than the treatment start hour value, and the AE is a TEAE if the AE start hour value is larger than the treatment start hour value
- 2i. otherwise, if the AE start hour value is equal to the treatment start hour value, but the AE start minute value is missing, the AE is a TEAE

Number	BIG-CL-SP-000319		
	IG1601 Statistical Analysis Plan		
GRIFOLS		Bioscience Industrial Group	
09-Sep-2024		50 of 52	

GRIFOLS	Bioscience Industrial Group	Number	BIG-CL-SP-000319	
		IG1601 Statistical Analysis Plan	Version	2.0
Effective Date	Page	51 of 52	Effective	09-Sep-2024

2j. otherwise, when the AE start minute value is not missing, it is a non-TEAE if the AE start minute value is less than the treatment start minute value, and the AE is a TEAE if the AE start minute value is equal to or larger than the treatment start minute value

2k. otherwise, if the AE status cannot be determined in steps 2a)- 2j), the AE would be treated as a TEAE

The procedure can be similarly applied to the SMT group except that the randomization date/time instead of the treatment start date/time is used in the SMT arm.

Appendix 3 – Region in Europe Categories

Region in Europe	Countries
West Europe	Belgium, France, Germany, Denmark, Spain, Italy, United Kingdom
East Europe	Bulgaria, Bosnia - Herzegovina, Hungary, Poland, Serbia

Appendix 4 – Visit Mapping for early discontinuation visit

Table 1: Scheduled Visits and Analysis Visit Windows for ALCF, CLIF-C OF Score and Sub Scores, CLIF-C ACLF Score, CLIF-C AD Score, MELD Score, Child Pugh Score, Child Pugh Sub Score, Child Pugh Class, Serum Albumin Concentration

Analysis Period	Scheduled Time Point	Analysis Visit (label on output)	Target Time Point (Day*)	Analysis Visit Window (Day)*
Baseline	Day 1	Baseline	1	<=1
	Day 11	Day 11	11	[2 to 21]
	Day 31 (Month 1)	Day 31 (Month 1)	31	[22 to 46]
			61	[47 to 76]
	Day 61 (Month 2)	Day 61 (Month 2)		
	Day 91 (Month 3)	Day 91 (Month 3)	91	[77 to 106]
	Day 121 (Month 4)	Day 121 (Month 4)	121	[107 to 136]
	Day 151 (Month 5)	Day 151 (Month 5)	151	[137 to 166]
	Day 181 (Month 6)	Day 181 (Month 6)	181	[167 to 196]
	Day 211 (Month 7)	Day 211 (Month 7)	211	[197 to 226]
	Day 241 (Month 8)	Day 241 (Month 8)	241	[227 to 256]

	Day 271 ((Month 9)	Day 271 ((Month 9)	271	[257 to 286]
	Day 301 (Month 10)	Day 301 (Month 10)	301	[287 to 316]
	Day 331 (Month 11)	Day 331 (Month 11)	331	[317 to 346]
	Day 361 (Month 12)	Day 361 (Month 12)	361	[347 to 376]

*Relative to Study Day 1.

Note: For Serum Albumin Concentration this is the Day 1 pre-dose visit

Table 2: Scheduled Visits and Analysis Visit Windows for Albumin Functional Capacity in Serum (Albumin Binding Capacity)

Analysis Period	Scheduled Time Point	Analysis Visit (label on output)	Target Time Point (Day*)	Analysis Visit Window (Day)*
Baseline	Day 1	Baseline	1	<=1
	Day 11	Day 11	11	[2 to 21]
	Day 31 (Month 1)	Day 31 (Month 1)	31	[22 to 46]
			61	[47 to 76]
	Day 61 (Month 2)	Day 61 (Month 2)		
	Day 91 (Month 3)	Day 91 (Month 3)	91	[77 to 106]
	Day 121 (Month 4)	Day 121 (Month 4)	121	[107 to 136]
	Day 151 (Month 5)	Day 151 (Month 5)	151	[137 to 166]
	Day 181 (Month 6)	Day 181 (Month 6)	181	[167 to 196]
	Day 211 (Month 7)	Day 211 (Month 7)	211	[197 to 226]
	Day 241 (Month 8)	Day 241 (Month 8)	241	[227 to 256]
	Day 271 ((Month 9)	Day 271 ((Month 9)	271	[257 to 286]
	Day 301 (Month 10)	Day 301 (Month 10)	301	[287 to 316]
	Day 331 (Month 11)	Day 331 (Month 11)	331	[317 to 346]
	Day 361 (Month 12)	Day 361 (Month 12)	361	[347 to 376]

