7.2.1.2.2 TREATMENT DAY 11 AND MONTHLY VISITS (MONTH 1 THROUGH MONTH 11)

Subjects will have assessments on Day 11 (± 2 days), Month 1 (± 2 days), and then monthly (± 2 days) for up to 11 months: Days 31, 61, 91, 121, 151, 181, 211, 241, 271, 301, 331.

All assessments and activities will be performed prior to treatment. In the SMT + Albutein 20% treatment group, vital signs and serum albumin concentration will also be recorded after treatment. Study assessments and activities will include:

- Record vital signs (systolic and diastolic BP, HR, RR, T) (measured immediately prior to and immediately after the end of the Albutein 20% infusion in the SMT + Albutein 20% treatment group)
- Ascites assessment according to the ICA criteria (Appendix 2)
- Hepatic encephalopathy evaluation (Appendix 4)
- Hemodynamics assessment (MAP)
- Peripheral capillary oxygen saturation (SpO₂) assessment
- Assessment of TIPS insertion
- Record weight
- Blood sample collection for (see Table 7-1):
 - Clinical laboratory assessments (eg, hematology, chemistry, coagulation)
 - Serum albumin concentration (measured immediately prior to and immediately after the end of the Albutein 20% administration in the SMT + Albutein 20% treatment group
 - Systemic inflammatory assessment
 - Albumin functional capacity assessment (albumin binding capacity [Day 11, Months 1, 3, 6, and 9 only])
 - Blood biomarker retains (optional, all clinical blood samples will need to be drawn first) (Months 1, 3, 6, and 9 only)
- Record ACLF grade (see Table 2-1)
- Illness severity scores evaluation: CLIF-C OF score, CLIF-C AD score, CLIF-C ACLF score, MELD score, and Child Pugh score (Appendix 3).
- Physical examination (Month 6 only)
- Record concomitant medications
- Quality of life assessment (EQ-5D-5L health questionnaire [Appendix 5]) (Months 1, 3, 6, and 9 only)
- Record AEs
- Record data on liver transplantation, subject survival, and cause of death (Months 3 and 6 only)
- Albutein 20% infusion (SMT + Albutein 20% treatment group only)

7.2.1.2.3 SMT + ALBUTEIN 20% TREATMENT DAYS 21, 41, 51, 71, 81, 101, 111, 131, 141, 161, 171, 191, 201, 221, 231, 251, 261, 281, 291, 311, 321, 341, 351

Subjects in the SMT + Albutein 20% treatment group will receive infusions every 10 (\pm 2) days for up to 12 months in the study. Study assessments and activities will include:

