5.2.5 Month 12 / Early Discontinuation

All subjects will have assessments at Month 12 (Day 361 ± 2 days)/Early Discontinuation. Subjects in the SMT + Albutein 20% treatment group will receive an Albutein infusion at Month 12. All assessments and activities will be performed prior to treatment for SMT + Albutein 20% treatment group. In the SMT + Albutein 20% treatment group, vital signs and serum albumin concentration will also be recorded after Albutein infusion.

Subjects who discontinue from the study early will complete the assessments that are planned for the Month 12 visit.

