6.1.5 Visit Windows

For safety analyses (laboratory and vital signs data) and efficacy analyses, by-visit summaries and analyses will analyze assessments by visit as designated on the CRF; visit remapping based on study day to an analysis visit window won't be applied. Unscheduled visits will be excluded from by-visit summaries and analyses. The Early Discontinuation

GRIFOLS	Bioscience Industrial Group	Number	IG1601	Version	2.0	Status	Effective	Effective Date	09-Sep-2024	Page	20 of 52
		IG1601	Statistical Analysis Plan								

visit will be summarized as a separate visit, without adjusting for the timing of assessments for subjects that discontinue early.

For the analyses of exploratory endpoints, the early discontinuation visit will be mapped to an assessment visit. The mapping will be based on the timing of a subject's assessment visit, relative to their Study Day 1. A detailed list of the parameters and the mapping rules to be applied is provided in [Appendix 4](#).

For cases where multiple assessments are recorded for a parameter within a single visit window, the following rules will be applied for each parameter:

- If 2 or more assessments are mapped to the same visit window, then the non-missing assessment closest to the scheduled visit target day will be used in the analysis.
- If 2 assessments are equidistant from the visit target day, the later non-missing observation will be used in the analysis.

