9.3.2 CLIF-C OF Score and Sub Scores for Organ Function

CLIF-C OF score is evaluated monthly through Month 12 and will be listed.

The CLIF-C OF score system consists of six sub-scores for liver, kidney, brain, coagulation, circulatory, and respiratory organs/systems – each with values of 1, 2 or 3 with a higher number representing more severe disease. Each CLIF-C OF sub-score will be summarized as a categorical variable by treatment for each visit.

The total CLIF-C OF score is a discrete numeric value in the range of 6 to 18 (inclusive) and is defined as the sum of the six organ/system sub-scores. If an individual sub-score is missing, the total score will also be missing. The total CLIF-C OF score and change in total score from baseline to each scheduled post-baseline visit will be summarized, as a continuous variable, by treatment and scheduled visit. In addition, the total score change from baseline of scheduled visits for both treatment groups will be analyzed by MMRM, which includes change in total score from baseline as the dependent variable; treatment, visit, region (Europe or North America) and history of hospitalization for acute decompensation of liver cirrhosis (yes or no), treatment-by-visit interaction, region-by-visit interaction, and history of hospitalization for acute decompensation of liver cirrhosis-by-visit interaction as fixed effects; baseline and baseline-by-visit as covariates; and measures within-subject at each visit as a repeated measure. The model employs an unstructured covariance matrix for the within-subject dependence. If the model fails to converge, the mixed effects model with a compound symmetry correlation structure will be used.

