Serum albumin concentration and albumin binding capacity will be listed for each subject, and summarized by visit. A summary table will present descriptive statistics for original values and change from baseline by treatment, parameter and visit. For the SMT + Albutein 20% group and serum albumin concentration parameter, change from baseline to the pre-infusion timepoint will be summarized. Moreover, the difference between pre-infusion and post-infusion within each visit will also be summarized.

GRIFOLS	Number	IG1601	Version	2.0	Status	Effective	Effective Date	09-Sep-2024	Page	39 of 52
	IG1601	Statistical Analysis Plan								

In addition, change from baseline at each visit will be analyzed for visits with data collected for both treatment groups, in the same way as CLIF-C OF scores. Figures will be presented for means over time including the baseline visit for both albumin concentration and functional capacity.

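### The albumin binding capacity windows in SAP Appendix 4 create seven analysis visits that only early-discontinuation samples can fill, leaving 37 of 91 covariance parameters in the exploratory MMRM without data

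*SAP*

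**What the plan says.** **Schedule.** SAP Appendix 1, footnote p, says of binding capacity: "Assessed on Day 11 and Months 1, 3, 6, and 9". Protocol 7.2.1.2.2 gives the same list. A baseline sample is taken on Day 1, and a further one at Month 12 or early discontinuation. SAP 5.2.5 states: "Subjects who discontinue from the study early will complete the assessments that are planned for the Month 12 visit". After that, SAP 5.2.7 collects only transplant, survival and cause-of-death data.

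**Mapping.** SAP 6.1.5 says: "For the analyses of exploratory endpoints, the early discontinuation visit will be mapped to an assessment visit". Other visits keep their case report form label, and unscheduled visits are left out of by-visit analyses. If two assessments fall in one window, the one closer to the target day is used.

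**Windows.** Appendix 4 Table 2, headed "Scheduled Visits and Analysis Visit Windows for Albumin Functional Capacity in Serum" and specific to binding capacity, has 13 post-baseline rows (Day 11 and Months 1 to 12), the same grid as Table 1.

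**Model.** SAP 9.3.9 says that "change from baseline at each visit will be analyzed for visits with data collected for both treatment groups", by the method used for the CLIF-C OF score. That method (SAP 9.3.2) is an MMRM in which treatment, region, hospitalization history and baseline each interact with visit. On the covariance: "The model employs an unstructured covariance matrix for the within-subject dependence". Compound symmetry replaces it if the model fails to converge.

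**The concern.** Seven of the 13 rows in Table 2 have no scheduled binding-capacity sample. Scheduled samples keep their own label and unscheduled ones are excluded, so these rows can be filled only by subjects leaving the study.

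Two consequences follow. First, the model gains seven visit levels, each with its own treatment contrast, whose only direct data come from a few selected dropouts. Secondly, the unstructured matrix grows to include covariances that no subject can inform. The covariance model finally used could then depend on a table that does not match the schedule, and on how the software reports a degenerate fit.

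**Working it through.** The documents give no figure on this point, so there is none to reproduce.

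**Inputs**
- Windows: SAP Appendix 4 Table 2.
- Scheduled visits: Day 11 and Months 1, 3, 6, 9 and 12, from SAP Appendix 1.
- 410 subjects and 20% dropout: SAP 6.2.
- Assumptions not in the documents: early discontinuation is spread evenly over Days 2 to 362 (361 days), is equal in the two arms, and yields one sample per dropout.

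**1. Visits and covariance parameters**
- Off-schedule months: 2, 4, 5, 7, 8, 10 and 11, so 13 − 6 = 7.
- Unstructured matrix with 13 visits: 13 × 14 / 2 = 91 parameters.
- With 6 visits: 6 × 7 / 2 = 21 parameters.

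**2. Parameters that no subject can inform**
- Each subject has one early-discontinuation visit, so no one contributes to two off-schedule months: 7 × 6 / 2 = 21 pairs.
- No one has a binding-capacity value after early discontinuation, so each off-schedule month is also unpaired with every later scheduled visit. For Months 2, 4, 5, 7, 8, 10 and 11 that is 4 + 3 + 3 + 2 + 2 + 1 + 1 = 16 pairs.
- Total: 21 + 16 = 37 of 91. The rank of the expected information matrix agrees: 54 = 91 − 37. This count does not depend on the dropout rate.

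**3. Expected samples off schedule**
- Each of the seven windows covers 30 days: 7 × 30 = 210 days, and 210 / 361 = 58%.

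| Dropout | Subjects | Off-schedule samples | Per window |
|---|---|---|---|
| 10% | 41 | 41 × 210/361 ≈ 24 | 3.4 |
| 20% | 82 | 82 × 210/361 ≈ 48 | 6.8 |
| 30% | 123 | 123 × 210/361 ≈ 72 | 10.2 |

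- At 20%, 6.8 / 2 = 3.4 per arm per month.

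**4. Are these samples enough to fit the extra visits?**
- Each off-schedule month needs 5 mean parameters (intercept, treatment, region, history, baseline) plus a regression on 2 to 5 earlier scheduled values, so 7 to 10 in all. At 20% dropout there are about 6.8 subjects to fit them.
- Over 20,000 simulated sets of dropout times at 20%, an average of 5.7 of the 7 windows had no more subjects than parameters. At least one such window occurred in essentially all trials at 10% and 20%, in 99% at 30% and in 60% at 40%.
- One simulated trial at 20% dropout was fitted by maximum likelihood with the unstructured matrix. The likelihood kept rising, and the conditional variance collapsed to about zero in 6 of the 7 windows. Treatment estimates at the six scheduled visits were the same from two starting values.
- In one simulated trial at 60% dropout the likelihood settled, but the Month 2–Month 3 covariance came out as 0.655 or 0.610 depending on the starting value.

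**5. Does the both-arms condition remove these months?**
- At 20% dropout, 41 per arm, the chance that one arm has no sample in a given month is (1 − 30/361)^41 ≈ 0.03.
- Both arms have data with probability about 0.97² ≈ 0.94, so most of the seven months would qualify.

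**The case against.** A reader might infer that the specified model cannot be estimated at all. The documents do not support that. Covariances never observed together do not enter the likelihood, so contrasts at the six scheduled visits remain estimable in principle, and SAP 9.3.2 prespecifies compound symmetry as the fallback. Moving to that fallback is likely rather than certain: software may report convergence with a singular Hessian, in which case the stated trigger might not apply.

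The wording of the model can also be read narrowly. SAP 9.3.2 refers to scheduled visits and SAP 9.3.9 to visits with data in both arms. Read with Appendix 1, this could mean only the six scheduled visits. But Table 2 itself lists the seven months as scheduled time points, and the both-arms condition would seldom exclude them at the planned dropout. The ambiguity stands, and the SAP should resolve it.

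The sample counts are soft. The 20% is a sample-size allowance, not a forecast of early-discontinuation samples. Protocol 5.3.5 obtains withdrawal blood samples only where possible and directs the early-discontinuation procedures to subjects who received investigational product, whereas SAP 5.2.5 covers all subjects. The control arm may therefore supply fewer samples than assumed, and a death without a discontinuation visit supplies none. The count of 37 is unaffected.

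Finally, the endpoint is exploratory and lies outside the testing sequence in SAP 6.5. That limits the importance of the point but does not make the table right.

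**Conclusion.** The mismatch is clear and worth correcting. As written, Table 2 and SAP 6.1.5 create seven visits that only dropouts can populate and expand the covariance matrix from 21 to 91 parameters, 37 of them without data at any dropout rate. At the planned dropout the unstructured fit would probably degenerate or give way to compound symmetry, and treatment contrasts resting on about 3 to 4 dropouts per arm could be reported as monthly results.

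The estimate of about 48 off-schedule samples rests on even timing over 361 days, 20% dropout and one sample per dropout; the range is about 24 to 72 for 10% to 30% dropout. Only an exploratory analysis is affected; primary and secondary results do not depend on it.

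**What to change.** Limit Table 2 to the six scheduled post-baseline visits with contiguous windows, for example:

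| Visit | Window (study day) |
|---|---|
| Day 11 | 2–21 |
| Month 1 | 22–61 |
| Month 3 | 62–136 |
| Month 6 | 137–226 |
| Month 9 | 227–316 |
| Month 12 | 317–376 |

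Add to SAP 9.3.9 that only these six visits enter the binding-capacity MMRM. The matrix then has 21 parameters, and completers with full data inform every pair.

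The cost is one table and one sentence, with no change to data collection. There is a downside. Under the closest-to-target rule in SAP 6.1.5, an early-discontinuation value that follows an attended visit in the same window is still not used. If scheduled visits occur on target, this covers Days 47–61, 107–136, 197–226 and 287–316: 15 + 30 + 30 + 30 = 105 of the 210 off-schedule days. Some values will also be assigned to a visit up to about 45 days away. The widths are a choice that the sponsor may vary, provided that every window contains a scheduled sample.

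Neither Appendix 4 table in the text reviewed names EQ-5D-5L, which is analyzed by the same method (SAP 9.3.11), but that text may be incomplete after Table 2. If the full appendix has no EQ-5D-5L mapping, the same windows can be used without a separate Day 11 row.
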